12.0 Withdrawal of Participants

12.1 Withdrawal Circumstances: Participants will be able to discontinue study participation at any time. The participants may choose to discontinue stimulation at any time during the session if experiencing excessive discomfort or side effects. Criteria for discontinuation related to intervention: i) sores at the tDCS administration site; ii) headaches that impair global functioning. If subjects choose to stop their participation, they will be released from the study. To protect vulnerable populations, if a patient that was deemed capable of providing consent goes through unforeseeable situations that may affect their capacity to consent, their capacity will be reassessed, and if not deemed capable, they will be withdrawn from the study. Participants are also informed that study staff may terminate study participation at any point if they are concerned about the patient's welfare or behavior.

12.2 Withdrawal Procedures: Participants will be withdrawn from the study if they report any side effects of greater than moderate severity or that raise any safety concerns. Subjects may also be withdrawn from the study if they fail to follow study procedures (e.g., show up to scheduled study visits). Additionally, subjects will be told that participation is voluntary and that they may discontinue participation at any time for any reasons.

If participants withdraw from procedures, all their data collected until the withdrawal data will be retained. No new data will be collected from any private/protected record.

Participants who withdraw from the study after having received tDCS will be asked if they can be contacted by telephone to ascertain substance use status. We will attempt to contact participants by telephone who do not show up to scheduled visit to ascertain if they wish to continue to participate in the study (and if not, why not) and to determine substance use status.

12.3 Termination Procedures: If at any point research staff is concerned about participant's welfare or behavior, they will notify the participant that their participation in the study needs to terminate because of safety reasons. The participant will be paid for their time as per 11.4 until their last active participation day. Data collected until the termination date will be used and considered incomplete.

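### Section 15.3 models connectivity only before and after the intervention; it should name all three scans and all randomised participants in a likelihood-based model

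*Combined protocol and SAP*

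**What the plan says.** **Outcome and scans.** Section 3.1 schedules rest fMRI before the intervention, after five sessions and after the intervention, and defines the FC outcome as change over those imaging sessions. Its A2 and A3 paragraphs compare pre-to-post change between arms. Section 5.1 gives statistical power for a trend over time as the reason for adding the midpoint MRI.

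**Analysis.** Sections 15.1 and 15.3 use two time points, before and after. Section 15.3 calls the method a mixed model analysis of variance, applied to FC and craving. It does not mention the midpoint scan or name cognition in that model, and it states no analysis set and no handling of missing scans.

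**People who leave.** Under 12.2, "all their data collected until the withdrawal data will be retained". Under 12.3, after termination by staff, "Data collected until the termination date will be used and considered incomplete". Later contact is by telephone: "Participants who withdraw from the study after having received tDCS will be asked if they can be contacted by telephone to ascertain substance use status", and those who miss a visit are also called "to ascertain if they wish to continue to participate in the study". Two routes out are "Participants will be withdrawn from the study if they report any side effects of greater than moderate severity" and "Subjects may also be withdrawn from the study if they fail to follow study procedures".

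**Order of assignment.** Section 5.2 describes random assignment under Visit One. The pre-intervention MRI is at Visits 2-3.

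**Cognitive battery.** Section 5.2 has the midpoint visits repeat the cognitive assessments of Visit Two, and the post-intervention visits repeat those of Visits 9-10. The lists of testing times in 3.2 and 5.1 omit the midpoint.

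**The concern.** The trial collects a scan that its analysis section does not use, and keeps data from leavers without saying how they enter the analysis. A classical pre-post ANOVA needs both scans from each person, so anyone without a post scan drops out of A2 together with the baseline and midpoint scans already obtained. That wastes precision. It also leaves two defensible analyses of one dataset, a completers' pre-post ANOVA and a three-scan model, with nothing to stop the choice being made after the results are seen.

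Attrition bias is possible as well. Only the active arm receives sustained current, and side effects above moderate severity lead to withdrawal from the study, so retention could differ by arm. If leavers would also have changed differently from stayers, a completers' contrast is shifted.

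**Working it through.** The protocol gives no power, dropout or variance figure for this trial (15.2), so there is none to reproduce. Every rate and correlation below is an assumption. The 15 per arm is half of the 30 completers mentioned only in the revision history.

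**1. Variance.** Let the three scans have equal variance and common correlation r, and let a share p of an arm have the post scan. Let R² be the share of variance in pre-to-post change explained by the scans leavers already have. In large samples, the variance of the likelihood estimate relative to completers-only is 1 - R²(1 - p).

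- With baseline and midpoint: R² = 1/(2(1 + r)), which is 0.357 at r = 0.4 and 0.278 at r = 0.8.
- Largest gain: r = 0.4, p = 0.75: 1 - 0.357 × 0.25 = 0.911.
- Smallest gain: r = 0.8, p = 0.90: 1 - 0.278 × 0.10 = 0.972.

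The reduction is therefore about 3-9%. It supposes that every leaver has the midpoint scan and that the correlations are known; estimating them at 15 per arm gives back part of it. At p = 1 the ratio is 1, so the gain in this contrast comes only from people who leave.

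With the baseline scan alone, R² = (1 - r)/2. At r = 0.6 and p = 0.75 the ratio is 1 - 0.20 × 0.25 = 0.950 without the midpoint, and 1 - 0.3125 × 0.25 = 0.922 with it. Both parts of the change contribute.

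**2. Completers-only bias with no true effect.** Bias = ρ[φ(z_A)/p_A - φ(z_S)/p_S], where ρ is the correlation between staying and change (0.2 or 0.5), p_A and p_S are retention in the active and sham arms, and z is the normal quantile of p.

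| Retention, active vs sham | Bracket | ρ = 0.2 | ρ = 0.5 |
|---|---|---|---|
| equal | 0 | 0 | 0 |
| 85 vs 90% | 0.274 - 0.195 = 0.079 | 0.016 | 0.040 |
| 80 vs 90% | 0.350 - 0.195 = 0.155 | 0.031 | 0.078 |
| 75 vs 90% | 0.424 - 0.195 = 0.229 | 0.046 | 0.114 |

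Units are SD of change. Swapping the arms, or letting leavers be those who would have changed more, reverses every sign. The range at these gaps is therefore about -0.11 to +0.11 SD. The standard error at 15 per arm is √(2/15) = 0.365 SD, so the largest value is 0.114/0.365 = 31% of one standard error.

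**3. What the three-scan model does to that bias.** If withdrawal depends on observed midpoint change, simulation puts the remainder within 0.002 SD of zero. If it tracks the unseen final change, the share left is approximately 1 - R² = (1 + 2r)/(2(1 + r)): 0.64, 0.69 and 0.72 at r = 0.4, 0.6 and 0.8. Simulation at r = 0.6 gave 0.69-0.73, and 0.72-0.76 if half of the withdrawals fall in the first block. About 70% remains.

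**4. Assignment before the scan.** If N are assigned equally and 30 are scanned with losses unrelated to arm, the expected variance inflation from uneven arms is approximately (1/30)(N - 30)/(N - 1). For N = 34, 38, 44 and 50 this is 0.4%, 0.7%, 1.1% and 1.4%. There is no bias while blinding holds.

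**The case against.** The strongest reply is that the plan may already mean what is asked. A mixed model can be likelihood-based, 12.3 says data up to termination will be used, and 3.1 and 5.1 show that the midpoint scan was meant to count. This is a pilot without a power analysis, the precision gain is modest, and 5.2 lists retention steps (several contact numbers, calls, reminder cards, texts). All of that stands as a limit on size. It does not settle the method: 15.3 names two time points, and a classical ANOVA is an equally natural reading.

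A reader might infer more than the documents support:

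- *That attrition favours active tDCS.* No section says which arm will lose more people or that leavers change less. Both arms feel the ramp, and 13.1 expects mild effects that typically resolve.
- *That assessment after withdrawal is forbidden.* Section 12.2 is silent. Section 12.1 separates stopping within a session ("The participants may choose to discontinue stimulation at any time during the session") from leaving ("If subjects choose to stop their participation, they will be released from the study"), but does not say whether someone who stops stimulation only still attends Visits 16-17.
- *That A2 and A3 must rest on completers.* Retained data and the midpoint scan make partial use possible. For A3, the weekly constant-difficulty 3-back tasks in 4.0 also give some on-treatment data.
- *That a cap of 250 consented against 30 completers implies heavy dropout.* That gap includes screen failures.
- *That assignment at Visit One biases the comparison.* It costs a little efficiency. Section 8.3 asks about MRI compatibility before consent, which limits the losses.

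**Conclusion.** The point holds as a gap between 15.3 and sections 3.1 and 5.1. As written, the analysis does not use a scan that the trial collects for power, and on its classical reading it discards retained data from anyone without a post scan. The likelihood-based three-scan model is better and uses data already collected. Its gain is about 3-9% lower variance for the pre-to-post contrast at r = 0.4-0.8 and 75-90% retention, somewhat less in small samples and nothing at full retention.

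It is only a partial remedy for bias: complete if withdrawal depends on observed data, with about 70% left if withdrawal tracks the unseen final change. The bias itself is of unknown sign, zero at equal retention and mechanism, and at most about 0.11 SD either way at the assumed gaps. The matter is worth considering and does not threaten the trial. Assignment timing and the cognitive-battery wording are minor.

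**What to change.** 1. In 15.3, state that FC is analysed in all randomised participants by assigned arm, with a likelihood-based mixed model using the baseline, midpoint and post scans. Keep the pre-to-post group contrast for A2.
2. Report withdrawals by arm over the number randomised, and acknowledge that withdrawal depending on unobserved change is not covered by the model.
3. Minor: carry out assignment after MRI approval and the baseline scan, before the first tDCS session, so that nobody is randomised without a baseline FC.
4. Minor: reconcile 5.2 (Visits 9-10 and 16-17) with the lists in 3.2 and 5.1 on whether the cognitive battery is given at midpoint.

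The cost is one amendment and moving the assignment step by a visit or two. No additional scans or visits are needed, and all stopping, safety, welfare and capacity rules stay as they are.

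MRI and cognitive visits after withdrawal are an optional design preference and not part of this fix. They would need extra resources, would not reach participants withdrawn from the study for side effects, and would overlap the 12.2 provision on missed visits.

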13.0 Risks to Participants

13.1 Foreseeable Risks:

TDCS is considered to be a safe brain stimulation technique that rarely results in adverse events. There is currently no evidence of serious side-effects. Mild side-effects

PROTOCOL TITLE: Combining Neuro-Imaging and Non-Invasive Brain Stimulation for Clinical Intervention in Opioid Use Disorder

VERSION DATE: 2022-02-11

that typically resolve upon discontinuing tDCS include light itching under the electrode at the beginning of administration, headache, fatigue, and nausea. The subject may choose to discontinue stimulation at any time during the session if experiencing excessive discomfort or side effects. Although seizures are not a known risk of tDCS intervention (Fregni et al. 2006), anyone with a history or a risk for seizures will be excluded from the study. No other risks related to tDCS are anticipated. To minimize risks regarding tDCS, study staff will be using standards of administration that have been shown as safe in numerous other studies using transcranial direct current stimulation. The length of administration of the current, size of electrode sponges used, and method of applying stimulation are the same as methods of administration that have been demonstrated as safe.

The other potential risks pertain to the maintenance of confidentiality. Participants will be probed for personal information during the interviewing process. As noted in the consent form, participants will be told that all diagnostic and other sensitive raw data will be kept in a locked file and available only to authorized investigators involved in this study. To minimize confidentiality risks, as noted in the consent form, all diagnostic and other sensitive raw data will be kept in a locked file and be available only to authorized investigators involved in this study.

MRI risks. Individuals will complete a screening questionnaire for contraindications of MRI scanning. Any affirmative responses on the questionnaire will result in an interview regarding the possible contraindication. An attempt will be made to secure any records of the nature of the possible contraindication and this information will be reviewed by the PI and CMRR staff at the University of Minnesota. A determination will be made regarding the level of risk to the subject and whether they are approved for scanning. If approved for scanning by professionals, all risks to the subject will be conveyed to him or her so they can deliberate as to whether or not they want to complete the procedure. Any concerns from the review committee will be conveyed to the participant at that time. If the subject has certain problematic iron or steel implants in their body that cannot be removed, the subject may not have the scan and will be excluded from the study.

There are no known risks to humans due to the static magnetic field. Subjects, operators, and guests are carefully screened prior to entering the magnetic environment, and frequently reminded of the potential danger of introducing magnetic objects to the controlled area. Subjects are carefully screened and excluded from the study if they have any implanted devices. Subjects are always accompanied when near the magnet, and reminded to move slowly and carefully as they enter and leave the magnet.

The risk of tissue damage by energy emitted by the MRI device is controlled by compliance with FDA guidelines for commercial MRI devices. Safety devices are in place so that the magnet will cease to operate should any parameters begin to exceed their preset safety limits. The risk of peripheral nerve stimulation by dB/dt is limited by safety devices. The noise levels generated by each scan are

PROTOCOL TITLE: Combining Neuro-Imaging and Non-Invasive Brain Stimulation for Clinical Intervention in Opioid Use Disorder

VERSION DATE: 2022-02-11

monitored to ensure adherence to guidelines. In addition, subjects are provided with earplugs and secondary protection (foam covering or headphones) to increase comfort during the scan.

13.2 Reproduction Risks: Since the MRI risks to fetuses are unknown, pregnant women are excluded from the study. Female subjects in child-bearing years will be informed that their consent to participate indicates that they are willing to complete a urine pregnancy test to demonstrate that they are not pregnant.

13.3 Risks to Others: N/A

14.0 Potential Benefits to Participants

14.1 Potential Benefits: No benefit is guaranteed for the subject from being in this study, yet some individuals may feel rewarded by contributing to science.

15.0 Statistical Considerations

15.1 Data Analysis Plan: Compare brain FC between groups: Sham vs Active tDCS. Compare FC within groups to examine time effects: before and after intervention. Look for interaction effects (group x time).

15.2 Power Analysis: The study in reference is a pilot study for which a power analysis is not applicable.

15.3 Statistical Analysis: A mixed model analysis of variance will be conducted with between-group measures (sham vs active tDCS) and within-group measures (FC and craving reports before and after cognitive training and tDCS intervention). This mixed model analysis will examine main- and interaction-effects. To examine the long-term effects of cognitive training and tDCS, we will conduct a repeated measures analysis using longitudinal data collected at 1- and 2-month follow-up timepoints after intervention completion. A Log-rank (Mantel-Cox) Test (used in (Klauss et al. 2014) will be conducted to establish the efficacy of cognitive training and active tDCS vs. cognitive training and sham tDCS in the time domain.

15.4 Data Integrity: The principal investigator and co-investigator will monitor data quality for this study. They will ensure that data are generated, documented (recorded), and reported - in compliance with this protocol, with Good Clinical Practice, and any other applicable regulatory requirements.

PROTOCOL TITLE: Combining Neuro-Imaging and Non-Invasive Brain Stimulation for Clinical Intervention in Opioid Use Disorder

VERSION DATE: 2022-02-11

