1.0 Objectives

1.1 Purpose: The overarching goal of this project is to expand the traditional expertise in non-invasive neuromodulation at the University of Minnesota towards developing novel paired-neuromodulation approaches using tDCS for new addiction treatments that support long-term abstinence. This study will allow us to investigate whether the pairing of DLPFC stimulation and cognitive training can enhance FC between DLPFC and NAcc. We have identified higher FC between DLPFC and NAcc in alcoholics that have successfully maintained abstinence for extended periods of time (7 years). This paired-neuromodulation approach can potentially be used as a therapeutic intervention to decrease substance use probability in addiction (e.g. opioid use disorder). The long term goal is to develop new addiction treatments that support long-term abstinence in opioid use disorder. The overall objective of this proposal is to enhance FC between DLPFC and NAcc as a therapeutic intervention to enhance cognition and reduce substance use rates in opioid use disorder.

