3.0 Study Endpoints/Events/Outcomes

3.1 Primary Endpoint/Event/Outcome: In a double-blind randomized design, up to 250 individuals with a current opioid use disorder (OUD) diagnosis, age 18-60 years, enrolled in a methadone or buprenorphine treatment program and

PROTOCOL TITLE: Combining Neuro-Imaging and Non-Invasive Brain Stimulation for Clinical Intervention in Opioid Use Disorder

VERSION DATE: 2022-02-11

clinically stable will be recruited. We will recruit individuals who have been treatment with methadone or buprenorphine for at least 2 months. Patients will receive 10 sessions (2 5-day blocks of 46-minute daily tDCS intervention) of either (i) transcranial direct current stimulation (tDCS) to PFC or (ii) sham-tDCS. All subjects will perform cognitive training during tDCS intervention (active or sham) to prime the engagement of the NAcc-PFC brain circuit. Rest fMRI will be collected pre-intervention, after 5 sessions, and post-intervention. Follow-up interviews will be conducted 1- and 2-months after intervention completion to assess cognition, assess behavior, and query substance use. Dependent variables will be (i) change in NAcc-PFC FC across intervention imaging sessions, (ii) change in cognitive performance across intervention sessions, and (iii) substance use status 2 months after study participation. The Specific Aims are to determine if the intervention: (A1) is feasible and safe in individuals with OUD, (A2) induces circuit-based target engagement (an NIH funding requirement), (A3) induces cognitive performance changes, and (A4) is related to substance use status 2 months after study.

To evaluate feasibility (A1), withdrawal and retention policies are described in Section 12.0. To evaluate safety (A1), we will use the Treatment Side Effects Questionnaire to record intervention side effects. Based on our alcohol tDCS study and studies from other research groups, we hypothesize that the intervention will be feasible and safe.

To evaluate circuit-based target engagement (A2) we will compare brain activation change (from pre-intervention to post-intervention) between active tDCS and sham groups. We hypothesize that the active tDCS group will have a larger increase in brain circuit engagement than the sham group.

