4.2 Biosafety: N/A

4.3 Stem Cells: N/A

5.0 Procedures Involved

5.1 Study Design:

This study is double-blind, within subject, within study staff, and sham-controlled. The scientific integrity of the trial and the credibility of the data from the trial depend substantially on the trial design. A description of the trial design includes: In a double-blind randomized design, up to 250 individuals with a

PROTOCOL TITLE: Combining Neuro-Imaging and Non-Invasive Brain Stimulation for Clinical Intervention in Opioid Use Disorder

VERSION DATE: 2022-02-11

current opioid use disorder (OUD) diagnosis, age 18-60 years, enrolled in a methadone or buprenorphine treatment program and clinically stable will be recruited. Patients will receive 10 days (1 20-minute administration per day) of either (i) transcranial direct current stimulation (tDCS) to PFC or (ii) sham-tDCS. All subjects will perform cognitive training during tDCS intervention (active or sham) to prime the engagement of the NAcc-PFC brain circuit. Rest fMRI will be collected pre-intervention, at the midpoint of intervention, and post-intervention. The purpose for adding the midpoint MRI is to increase the statistical power of showing the trend of the experimental treatment's effectiveness over time. Follow-up interviews will be conducted 1- and 2-months after intervention completion to query substance use.

To examine generalization and durability effects of training, patients will be asked to complete the following tasks at pre-intervention, post-intervention, 1-month follow-up and 2-month follow-up: D-KEFS Trail Making Test, D-KEFS Verbal Fluency, D-KEFS Color Word, Digit-Span (WAIS-WISC), Intra-Extra Dimensional Set-Shift Task. Saliva/Urine tests checking for substance use will be administered at each follow-up timepoint.

5.2 Study Procedures:

Randomization: Random permuted blocks (subgroups of 4) will be used to ensure equal group assignment (active or sham tDCS) at predefined equally spaced points in the sequence of patient assignment. Blinding: Participants will not be informed on their assigned protocol. During consent, they will be informed that there is a 50% chance of receiving active tDCS or sham tDCS every visit for five study visits.

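### The midpoint MRI is justified by power in Section 5.1 but enters no named analysis, and the planned pre/post ANOVA gives up the precision of adjusting for the baseline scan

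*Combined protocol and SAP*

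**What the plan says.** Section 5.1 gives the reason for the extra scan: "The purpose for adding the midpoint MRI is to increase the statistical power of showing the trend" of the treatment effect over time. Section 3.1 confirms three imaging sessions: "Rest fMRI will be collected pre-intervention, after 5 sessions, and post-intervention". It defines the first dependent variable as "change in NAcc-PFC FC across intervention imaging sessions".

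The analyses themselves name only two time points:

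- Section 3.1, Aim 2: "we will compare brain activation change (from pre-intervention to post-intervention) between active tDCS and sham groups".
- Section 15.1: "Compare FC within groups to examine time effects: before and after intervention", followed by a group-by-time interaction.
- Section 15.3: a mixed model ANOVA with "within-group measures (FC and craving reports before and after cognitive training and tDCS intervention".
- Section 15.3, separately: a "repeated measures analysis using longitudinal data collected at 1- and 2-month follow-up timepoints after intervention completion". Section 5.2 describes those visits as questionnaires, cognitive tasks and drug tests, without MRI.
- Section 15.3 also has a log-rank test, which is a time-to-event analysis.

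No baseline covariate is mentioned. Section 15.2 says that a power analysis does not apply because this is a pilot. Sections 12.2 and 12.3 keep data collected up to withdrawal or termination. Nothing says how a participant without a post-intervention scan enters the analysis of functional connectivity (FC).

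**The concern.** Participants attend a third MRI session for a statistical reason that no named analysis carries out. It is left open whether time has two or three levels in the FC model. That choice bears on Aim 2, target engagement, which Section 3.1 calls a funding requirement, and it should not be made after the data are seen. Craving is in the same pre/post ANOVA and is also re-assessed at the midpoint.

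The test that is named also leaves information unused. In a small pilot, the baseline scan is the cheapest source of precision, and an unadjusted change-score comparison does not use it fully. The stakes are efficiency and pre-specification. The planned test is not biased, and no stated power target is missed because none is set.

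**Working it through.** **Inputs.** From the documents: three scans, 1:1 allocation and a pre/post group-by-time test. The goal of 30 completers appears only in the amendment log and is used here as a planning figure, 15 per arm. Assumed, because the documents do not give them: two-sided 5% level, equal variances over time, and pre-post correlation r = 0.3, 0.5 or 0.7 (0.9 as an extreme).

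**Check on the same type of test.** The plan has no power figure for this trial to reproduce. For the alcohol pilot in Section 2.2 (6 against 5), F(1,9) = 7.105 gives p = 0.0258 and eta-squared = 7.105/(7.105 + 9) = 0.441, matching the stated 0.026 and 0.441.

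**Baseline adjustment.** In units of the single-scan variance, the per-participant variance is 2(1 − r) for the change score and 1 − r² after adjustment. The ratio is (1 − r²)/[2(1 − r)] = (1 + r)/2. At 15 per arm, the change-score test F(1,28) needs noncentrality 4.120 for 50% power and 8.424 for 80%. Dividing by the ratio and using F(1,27) gives the formula columns. The cost columns also divide by 1 + 1/(30 − 4) = 1.038 for estimating the covariate.

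| r | Variance ratio | From 50%: formula | From 50%: with covariate cost | From 80%: formula | From 80%: with covariate cost |
|---|---|---|---|---|---|
| 0.3 | 0.65 | 68.0% | 66.3% | 93.4% | 92.6% |
| 0.5 | 0.75 | 61.8% | 60.2% | 89.8% | 88.7% |
| 0.7 | 0.85 | 56.5% | 54.9% | 85.9% | 84.6% |
| 0.9 | 0.95 | 51.9% | 50.4% | 81.9% | 80.4% |

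Simulation of the proposed mixed model with complete data (8,000 trials) gave 65.7/60.2/54.9% at r = 0.3/0.5/0.7 from 50%, with type I error 5.2–5.3%.

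**Adding the midpoint as a third ANOVA level.** Let f be the fraction of the effect present after 5 sessions. With equal correlations, the noncentrality relative to the two-level test is the sum of squares of (0, f, 1) about its mean, divided by 0.5. The test is F(2,56).

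| f | Noncentrality ratio | From 50% | From 80% |
|---|---|---|---|
| 0.5 (linear) | 1.000 | 40.7% | 71.7% |
| 0.75 | 1.083 | 43.6% | 75.3% |
| 1 | 1.333 | 52.1% | 84.0% |

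The three-level test wins only if f is at least about 0.95 (from 50%) or 0.89 (from 80%), or, by symmetry about 0.5, almost zero. The 1-df linear trend has weights (−1, 0, 1), so the midpoint gets zero weight. Its power is 51.4% (81.4% from 80%), and the small rise comes only from extra error degrees of freedom.

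If nearer scans correlate more strongly (adjacent correlation √r), a multivariate F(2,27) test gives 38.6% for a linear effect. If the whole effect is present at midpoint, it gives 58.5/61.5/64.2% at r = 0.3/0.5/0.7. So whether the third scan adds power depends on when the effect appears.

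**Averaging midpoint and post, with baseline adjustment, from 50% (formula).** Equal correlation gives 64.1/54.6/47.4% for a linear effect and 87.1/79.0/71.4% for a full effect at midpoint. With decaying correlation the figures are 61.5/55.5/51.0% and 85.2/79.9/75.4%. The gain depends on an early effect, so this contrast suits a secondary role.

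**Missing post scans.** Assume 20% are missing completely at random and the effect is linear (3,000 simulated trials, from 50%).

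| Analysis | Equal correlation, r = 0.3/0.5/0.7 | Decaying correlation, r = 0.3/0.5/0.7 |
|---|---|---|
| Proposed mixed model | 55.6/49.5/46.4% | 57.0/52.9/48.7% |
| Complete-case, baseline-adjusted | 55.2/48.8/45.7% | 53.9/49.4/44.4% |

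The complete-case change score gives 40.3–41.9% across these settings. The difference between the table's rows is the midpoint's own contribution: under 1 point with equal correlation and 3 to 4 points with decay.

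**The case against.** The strongest reply is that two points are joined here. The mismatch between sections is a matter of record, but preferring baseline adjustment to a change score contradicts nothing in the plan, and Section 15.2 disclaims power for a pilot. It is true that no requirement is missed. But Section 5.1 itself invokes power, and the adjustment uses a value already collected at no cost, so it is more than a matter of taste.

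Second, the outcome in Section 3.1, "change in NAcc-PFC FC across intervention imaging sessions", could include the midpoint, and the before-and-after wording could be shorthand. That reading is possible, but no model is attached to the phrase, and Aim 2 is explicitly pre to post.

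Third, the size of the gain depends on anchors. It disappears near r = 0.9, as the table shows. The starting powers of 50% and 80% are illustrative. The alcohol pilot's effect, d = √[7.105 × (1/6 + 1/5)] = 1.61 on change scores, would give the planned test 98.9% power at 15 per arm. Three quarters of that effect gives 89% and half gives 57%. An 11-person study in another disorder is no planning value, but the need for extra precision does fall if the effect is that large.

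Fourth, the proposed Aim 2 test gains nothing from the midpoint when the data are complete. This stands, and it is why the sentence in Section 5.1 must change too.

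**Conclusion.** The concern holds, at the level of something that should be fixed. The text establishes that the midpoint scan enters no named analysis. That the two-level interaction test is less precise than a baseline-adjusted one follows for any r below 1, apart from the small covariate cost. The size of the loss is uncertain because the documents do not report r. At 15 per arm, a 50% power would rise by about 16, 10 or 5 points at r = 0.3, 0.5 or 0.7 after the covariate cost, and by almost nothing at 0.9. The midpoint scan contributes little to a post-scan test, so the power rationale in Section 5.1 is not assured by the planned analysis or by simply adding a third level.

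**What to change.** In Sections 15.1 and 15.3, replace the pre/post ANOVA for FC and craving with:

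> FC and, separately, craving at midpoint and post-intervention will be analysed in a linear mixed model with arm, time point, arm × time point, pre-intervention value and pre-intervention value × time point, unstructured covariance and Kenward-Roger degrees of freedom, including every randomised participant with a pre-intervention value and any later value. The A2 test is the adjusted active-minus-sham difference in NAcc-PFC FC at the post scan, with 95% CI. The midpoint-post average is secondary.

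State the same post-scan contrast for Aim 2 in Section 3.1. The within-group comparisons in Section 15.1 can stay. In Section 5.1, replace the power sentence with:

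> The midpoint MRI describes the time course, supports the secondary averaged contrast and keeps participants without a post scan in the model; any power gain depends on how early the effect appears.

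Three details need settling at the same time:

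- Confirm the region. Section 3.1 names PFC, while Section 1.1 aims to "investigate whether the pairing of DLPFC stimulation and cognitive training can enhance FC between DLPFC and NAcc".
- Name the pre-intervention craving value, since Section 5.2 collects craving at Visit 1 and again at Visits 2-3.
- Report by arm those randomised at Visit 1 who never reach the baseline scan.

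**Cost.** The change is wording in four sections, with no new data or participants. The covariate uses one degree of freedom per time point, about 2 power points at 15 per arm. The model assumes that missing scans are missing at random. It needs software with Kenward-Roger: with 20% of post scans missing, simulated type I error was 4.6–5.7% with it and 6.1–7.1% with a normal reference. The stated case for the midpoint scan becomes less favourable.
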